Results of the above tests will be compared to age normed values. In addition, the difference in results between final test results and initial test results will be obtained for the cognitive functioning score of each subject. Mean and standard deviation of this difference for all 10 subjects will be calculated. These results will be used to determine whether individuals and the group as a whole demonstrated age normed changes in their cognitive functioning over the course of the six month trial. Neuropsychological testing will occur at both sites, KKI and CCHMC, and the deidentified results will be sent to KKI for analysis. There is no control group in this study of subjects who are not receiving study drug. The published test-retest standard deviations will be used to determine whether changes in testing results exceed expected test-retest changes in results.

Expected seizure rate can vary greatly both between subjects and for an individual. Subjects must be on the same AEDs for the past three months to join the study. Subjects whose seizures increase to the point where it is necessary to add another seizure medication, start the ketogenic or Atkins diet, or go for surgery to control their seizures will be removed from the study.

Quantitative EEG: An EEG will be done prior to starting study drug and at the end of the study while still on study drug. An asymmetry in power (roughly an integration of amplitude and frequency) in the affected side of the brain compared to the unaffected (or less affected) side of the brain, will be quantified as previously described (Hatfield et al., 2007; Ewen et al., 2009) for the quantitative EEG analysis. EEGs will occur at both sites, KKI and CCHMC, and the de-identified EEGs will be sent to KKI for analysis. The reason for this analysis is as a non-invasive biomarker of brain function which could be useful to develop as a marker of drug response. Quantitative EEG power analysis reflects an integration of the EEG activity amplitude and frequency. Therefore asymmetry of power on qEEG for these subjects reflects the increased slowing and decreased amplitude frequently seen in these patients interictally as their neurologic involvement progresses. Even patients with bilateral brain involvement have more involvement on one side than on the other side. Power asymmetry on qEEG has been shown to correlate with brain perfusion, brain atrophy, and SWS neuroscore, therefore, it has the potential as a biomarker responsive to

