monitor sirolimus treatment, both from the standpoint of safety and efficacy in a future larger clinical trial.

Seizure (motor seizures) number will be collected at each study visit and compared across visits. Seizure number will be recorded from the two months prior to joining the study at baseline (by history) and "since last visit" for all study visits. Seizure length and type, need for rescue medication, ER visit or hospitalization will also be recorded and compared across visits and at the end of the study (on drug) compared to the beginning of the study (prior to starting drug). There will be stopping rules for safety.

Clinical neurologic severity scores (neuroscores) will be collected at each study visit, using a scale developed and validated by KKI. The neuroscore is comprised the frequency of seizures, extent of hemiparesis, assessment of visual field cut, and degree of cognitive functioning with a total score of 15 possible (Kelly, Hatfield, Lin, & [name], 2005). Descriptive statistics for this measure will be reported in the form of median and range. Mann Whitney U Test will be used to assess whether a significant change in neuroscores has occurred after treatment compared to prior to treatment. Neuroscores will be collected at both sites, KKI and CCHMC, and the de-identified results will be sent to KKI for analysis.

The Neurologic Quality of Life (Neuro QoL) will be collected prior to starting study drug and at each study visit. Descriptive statistics for this measure will be reported in the form of median and range. Mann Whitney U Test will be used to assess whether a significant change in quality of life has occurred after treatment compared to prior to treatment. NeuroQoL will be collected at both sites, KKI and CCHMC, and the deidentified results will be sent to KKI for analysis.

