The quantification of the facial birthmark score developed and validated at the KKI will occur at the beginning of the study, prior to starting study drug, and when the subjects reach the endpoint of the study at six months' time while still on study drug (Waelchli et al., 2014). If the subject elects to enter the Extension Phase, the facial birthmark will be rated at each Extension Phase visit. Descriptive statistics for this measure will be reported in the form of median and range. Mann Whitney U Test will be used to assess whether a significant change in the facial birthmark has occurred after treatment compared to prior to treatment. Facial birthmark scoring will occur at both sites, KKI and CCHMC, and the de-identified results will be sent to KKI for analysis.

Biomarker Development: Spearman's rho will be used to assess for the strength, direction and significance of correlations between qEEG results and neuropsychological outcomes, NeuroQoL and the SWS Neuroscore. Significance will be taken at p<0.05.

All of these outcomes will be used to determine whether sirolimus is 1) sufficiently well tolerated in this small group of subject and 2) what outcome measures and biomarkers demonstrate preliminary evidence of being responsive to sirolimus. This information will be used to determine the advisability of proceeding with a larger multicentered study and aid in the selection of outcome measures and biomarkers to be part of that follow-up randomized placebo-controlled trial.

Sponsors (federal, state, foundation and industry support): National Institute of Health (NIH) Faneca 66 Foundation

Pfizer (study drug only)

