- A pharmacokinetic study will be done at the baseline visit. The subject will be started on a dose based on the recommended starting dose of mg/m2. The PK study results will be used to adjust their dose in order to get the patient to 4-6 ng/mL serum levels as quickly as possible. Subjects will be started on the study drug at study Visit 2. The PK results will be ready by study Visit 3 and the dose can therefore be adjusted. There will be no dose escalation. The dose will only change as indicated by the PK study or if the concentration of sirolimus is outside of the 4-6 ng/mL goal. The maximum dose will be 2 mg/day. If at the maximal dose, the sirolimus serum level is below the target level of 4-6 ng/ml, this result could impact the interpretation of the results if this subject has less of a response than other subjects. If it were to be the case that the majority of subjects are not able to reach this target range, then this trial will begin to evaluate safety and clinical trial measures for a lower than expected dose range of sirolimus as a treatment for cognitive impairments in Sturge-Weber syndrome. Furthermore, for each of the outcome measures we will plot the outcome versus serum level of the study drug. If there is a positive correlation between outcome and response, then this data would be used to select an optimal dose range to target in future trials.

The starting dose/m2 varies based on age and dosing strategy (often better tolerated when divided BID). Since our patients will be >3y, the starting dose should be 0.6mg/m2 q12h. We routinely do "miniPK" determinations using time 0, 1hour, and 3h post dose blood levels of sirolimus. Since with first dose the time 0 is 0, we will only draw the 1h and 3h levels. [name] at Cincinnati has an extensive background and multiple publications in this area and will do the PK analyses. While age-specific guidelines are usually appropriate to get to goal within 1 month, these patients may be on multiple anti-epileptics, some of which alter sirolimus metabolism. Most often, the metabolism is increased, meaning that levels decrease and patients who are "fully induced" for this particular CYP are likely to need 50% or more higher dosing than patients who are not on anti-epileptics. Subsequent levels will be trough levels done before their morning dose.

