Strength - Grip Strength Test (Hamilton, Balnave, & Adams, 1994)

PROMIS measures self-report of emotional functioning (Cella et al., 2007)

Each test in this panel is age normed. Therefore, even though subjects will be of different ages, the change in their performance as a percentage of the normed values will be relevant and comparable from subject to subject. There are also published test-retest standard deviations from which to ascertain how much of a change in score is needed for a change to be regarded as significant.

 Neuro-QOL scale will be collected at each visit. The Neurologic Quality of Life (Neuro QoL) will be collected prior to starting study drug and at each study visit. Descriptive statistics for this measure will be reported in the form of median and range. Mann Whitney U Test will be used to assess whether a significant change in quality of life has occurred after treatment compared to prior to treatment. NeuroQoL will be collected at both sites, KKI and CCHMC, and the de-identified results will be sent to KKI for analysis.

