5.7 Subject Discontinuation

All data acquired prior to termination for the reasons outlined below will be included in the primary analysis unless patient withdraws consent. Every effort will be made to conduct a final study visit with the participant and participants will be followed clinically until, if applicable, all adverse events resolve.

- Withdrawal of consent
- Withdrawal by the participant
- Withdrawal by the investigator
- Intercurrent illness or event that precludes further visits to the study site or ability to evaluate disease (for example, mental status change, large pleural effusion, large stroke).

Early Stopping Rules: If a participant experiences a significant decline in his or her health or wellbeing, the PIs may remove the participant from the pilot study. This decision will be promptly made on a case-by-case basis with careful discussion between the PIs, the parents and/or patient, and in consultation with the IRB. In some cases, it can be more medically destabilizing to remove the subject from the study drug. However, in any case where a significant decline in health may be attributable to the study drug, or in any case where it is determined that it may not be in the subject's best interest to remain on the study drug, then they will be removed from the study. A significant decline in health or wellbeing could include a loss of seizure control and/or the occurrence of intolerable side effects. Loss of seizure control is defined as an increase in seizure frequency and/or severity or use of emergency medications that warrant the initiation of a new seizure medication or treatment such as, Ketogenic/Atkins diet, surgery, or VNS. If there has been a loss of seizure control, then the subject will be removed from the study drug at that time, he or she will complete the ending assessments, and then the subject will be removed from the trial. Other stopping criteria are listed in Tables 1 and 2 above. Other removal criteria include: death, lost to follow-up, withdrawal of consent for any further data submission, or inability to complete follow up two years from the protocol completion. Early withdrawals within the first two months on the study drug will be replaced with a new study subject.

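### The only before-versus-after test named for neuroscore, Neuro QoL and facial birthmark treats the same subjects as two independent groups, which costs power for small to moderate changes if the paired values are positively correlated

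*Combined protocol and SAP*

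**What the plan says.** The Protocol Synopsis (Statistical Considerations) gives each of the three measures the same treatment: median and range, then a Mann-Whitney test. For the neuroscore, "Mann Whitney U Test will be used to assess whether a significant change in neuroscores has occurred after treatment compared to prior to treatment". For facial birthmark, "Mann Whitney U Test will be used to assess whether a significant change in the facial birthmark has occurred after treatment". For Neuro QoL, "Mann Whitney U Test will be used to assess whether a significant change in quality of life has occurred after treatment". Section 5.3 repeats all three under the laboratory tests and clinical procedures. Neither place, nor section 6, names a paired test for them.

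The Synopsis is explicit about the design: "There is no control group in this study of subjects who are not receiving study drug". For cognition the plan works within subjects: "the difference in results between final test results and initial test results will be obtained for the cognitive functioning score of each subject".

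The Schedule of Events (section 4.6) collects neuroscore and Neuro QoL at Visits 1 and 2, again at Visits 3 to 6, and at Visit 7 in the Extension Phase. The plan does not say which of these visits enter the test. The birthmark rating is fixed more closely: before drug, and at six months on drug.

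The Synopsis says that all the outcomes will be used to judge tolerability, to see which measures respond, and to "aid in the selection of outcome measures and biomarkers to be part of that follow-up randomized placebo-controlled trial".

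**The concern.** In a single-arm trial the values before and after treatment belong to the same people. A Mann-Whitney test discards that link and judges the change against the spread between subjects. The Synopsis and section 4.1 admit subjects aged 3 to 31, section 1.1 says that involvement varies greatly between patients, and the neuroscore includes hemiparesis, visual field and cognition. Differences between subjects should therefore be wide and should largely persist over six months, which is when ignoring the pairing costs most.

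Choosing outcomes for a later trial is one of the two primary objectives, and these measures feed that choice. The Synopsis lists neuroscore and birthmark as secondary outcomes, but also names them under the primary safety and tolerability outcome. A test that is insensitive to group change is therefore insensitive to worsening as well as to benefit.

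**Working it through.** **No figure to reproduce.** The sample size of 10 rests on availability and experience (section 6). The documents give no power, SD, before-after correlation or expected change for these measures. The 0.05 level appears only with the Spearman correlations. The following are therefore assumptions: ten pairs, bivariate normal data with equal variances, two-sided 5%, shift expressed in between-subject SD (σ), and correlation ρ from 0 to 0.7.

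**Why pairing matters.** The variance of a within-subject change is 2σ²(1 − ρ). An unpaired test in effect uses 2σ². At ρ = 0.5 the true variance is half of what the test assumes. A 0.5σ shift divided by the SD of the change, 0.5/√(2(1 − ρ)), is 0.35 / 0.42 / 0.50 / 0.65 at ρ = 0 / 0.3 / 0.5 / 0.7. A paired test gains from this and the unpaired test does not.

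**Simulation.** 100,000 replicates per cell with exact critical values: Mann-Whitney rejects at U ≤ 23 or U ≥ 77 (level 4.33%), signed-rank at a smaller rank sum ≤ 8 (level 4.88%). Repeat runs agree to within about one percentage point.

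| Shift | Mann-Whitney, ρ = 0 / 0.3 / 0.5 / 0.7 | Signed-rank, same ρ |
|---|---|---|
| 0 (false positives) | 4.3 / 2.0 / 0.8 / 0.2% | about 4.9% throughout |
| 0.5σ | 16 / 13 / 10 / 8% | 17 / 22 / 28 / 43% |
| 0.8σ | 35 / 33 / 32 / 31% | 35 / 46 / 60 / 81% |
| 1.0σ | 51 / 52 / 53 / 55% | 50 / 65 / 79 / 94% |

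At 0.5σ and ρ = 0.5 the Mann-Whitney test misses 100 − 10 = 90% and the paired test 100 − 28 = 72%. The choice of test accounts for 18 points; the rest comes from having ten subjects. At 2σ both tests have power near 100%.

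**Worked cases on whole-point scores.** Mann-Whitney p is asymptotic with continuity correction. The baseline sets are illustrative: 3 to 12 (one subject at each value); 5,5,6,6,6,7,7,7,8,8; and five subjects at 6 with five at 7.

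| Pattern | Baselines 3–12 | Baselines 5–8 | Baselines 6–7 | Signed-rank p |
|---|---|---|---|---|
| All ten shift by 1 | 0.49 | 0.07 | 0.002 | 2/2¹⁰ = 0.002 |
| Seven worsen by 1, three unchanged | 0.62–0.65 | 0.14–0.27 | 0.008–0.076 | 2/2⁷ = 0.016 |

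The ranges in the second row cover all 120 choices of which seven subjects change. With wide baselines a uniform shift goes undetected. With tightly clustered baselines the gap vanishes, and the Mann-Whitney p can fall below the paired one.

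**The case against.** The strongest reply is that little hangs on these p-values. That largely stands. No p-value rule selects outcomes. Section 6 bases a larger trial on serious adverse events and the cognitive trend, and would size it on the cognitive outcome with the greatest response. With ten subjects the paired test also misses most 0.5σ changes at correlation 0.5. It is also fair that every power figure rests on assumed correlation, SD and normality, and that at correlation 0 there is no loss.

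Three stronger readings are tempting, and the documents do not support them.

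- A reader might infer that deteriorating subjects could go unnoticed. Adverse-event review (section 5.0), the toxicity and removal rules (section 5.3) and the decline and seizure-control rules (section 5.7) deal with individuals, and none uses this test. Only the group comparison is weakened.
- A reader might infer a risk of false claims of benefit. Under positive correlation the error is conservative, so it yields fewer false positives.
- A reader might infer from section 5.7 that the last available value of an early leaver should serve as the endpoint. That section keeps data acquired before termination in the primary analysis but gives no last-value rule, and the birthmark endpoint is defined as six months while on drug. How to handle early leavers is a separate question.

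None of this makes an independent-samples test suitable for paired data.

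**Conclusion.** The named test does not fit the design for neuroscore, Neuro QoL and facial birthmark, and nothing else in the documents supplies a paired test for them. The mismatch is certain from the text. Its cost is conditional. With positive correlation of 0.3 to 0.7, ten normal pairs and two-sided 5%, power at 0.5σ falls from 22–43% to 13–8%, and the false-positive rate from about 5% to between 2% and 0.2%. The loss applies to improvement and worsening alike. It is absent at correlation 0 and can reverse when baselines are tightly clustered.

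The point does not reach the cognitive outcome, which already uses each subject's difference, or the section 6 conditions for a larger trial. It is worth correcting because these measures inform outcome selection and the tolerability judgement, and because correction is nearly free.

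**What to change.** In the Synopsis and section 5.3, replace the Mann-Whitney sentence for each measure with:

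> Each subject's change from baseline (the last value before the first dose: Visit 2 for neuroscore and Neuro QoL, the pre-drug rating for birthmark) to the six-month endpoint (Visit 6) will be tested with the exact two-sided Wilcoxon signed-rank test at 5%, using Pratt's method for zero changes and mid-ranks for ties. The number of pairs, the number of zero changes and the median within-subject change with a distribution-free interval will be reported.

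Section 5.3 says "Subjects will be started on the study drug at study Visit 2", so the Visit 2 neuroscore and Neuro QoL must be recorded before the first dose. For subjects who lose seizure control, section 5.7 says "he or she will complete the ending assessments, and then the subject will be removed from the trial"; list such values of early leavers descriptively, outside the test. With ten pairs, the interval from the 2nd to the 9th ordered change has coverage 1 − 22/1024 = 97.9%; with nine, the 2nd to the 8th gives 1 − 20/512 = 96.1%; with eight, the 1st to the 8th gives 1 − 2/256 = 99.2%.

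The cost is wording only: no new data, visits, subjects or staff. There are two small downsides. With five or fewer non-zero changes the smallest possible p is 2/2⁵ = 0.0625, so the median change and its interval become the result to read. And a correctly sized test raises the chance of at least one false positive across the three measures, if independent, to 1 − (1 − 0.0488)³ = 13.9%, from 1 − (1 − 0.008)³ = 2.4% for Mann-Whitney at correlation 0.5. The p-values should therefore be labelled exploratory.

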of warfarin or on a stable dose of LMW heparin for >2 weeks.)
of warfarin or on a stable dose of LMW heparin for >2 weeks.) 9. Adequate liver function as shown by:
of warfarin or on a stable dose of LMW heparin for >2 weeks.)

- 10. Written informed consent according to local guidelines. Local guidelines for subject assent will also be followed.
 11. Stable dose of medications affecting the cytochrome P 450 3A4 (CYP3A4) and p glycoprotein (P gp) systems for at least 3 months prior to consent.

Treatment				
Agent-	Rapamune® / Rapamycin® (sirolimus)			
Dosage,	Oral dose targeting a serum level dose range of 4-6 ng/mL given for a minimum of			
schedule, route of	six months. Dose based on surface age, surface area, and mini-PK as outlined in			
administration-	the protocol.			
	Subjects will receive no more than 2 mg/day given in two divided doses for a			
1	minimum of six months with the option to enter into the Extension Phase up to an			
	additional year and a half.			
Primary	Safety and Tolerability of sirolimus in patients with Sturge-Weber syndrome.			
Outcome	Adverse Events will be determined at every visit and on every phone call			
Measures:	using a case report with a list of side effects which can be seen with higher			
	doses and serum levels than are expected with this study. Impact of the			
	study drug upon seizure frequency, type, and duration will be assessed by			
	patient/parent report using a seizure report form we have used in a prior study. Impact of study drug upon neurologic, ophthalmologic, endocrine,			
	medical rehab, and dermatologic status will be assessed with case report			
	forms, the physical exam, the Sturge-Weber syndrome neuroscore, the port-			
	wine birthmark score, and other outcome measures described in the			
	protocol.			
	Change over six months in cognitive functioning in Sturge-Weber syndrome			
	is the primary outcome measure. This outcome will be assessed using a			
	panel of testing selected based upon extensive experience in testing			
	cognitive function in adults and children with SWS at the Kennedy Krieger			
	Sturge-Weber Center. These will include the following measures from the			
	National Institute of Health Toolbox (Gershon et al., 2010):			
	Attention/Executive Function – Flanker Inhibitory Control and Attention Test (Eriksen & Eriksen, 1974)			
	Executive Functioning – Dimensional Change Card Sort Test (Zelazo, Frye, & Rapus,1996)			

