5.9 Quality Control: Study Related Procedures

- 1. Clinical coordinators at both sites will review the case report forms after completion by [name] or [name] to resolve any issues.
- 2. [name] and [name] will review the study progress regularly with monthly phone conferences. The two sites will have internal reviews performed regularly to ensure high quality of the study procedures and subsequent data.
- 3. The DMCC will perform an audit of the overall protocol including this pilot project.

6. Statistical Considerations

The proposed trial is a pilot drug trial. Based on the results, a sample size calculation will be done, using the cognitive outcome with the greatest response to the study drug, to plan a follow up randomized, placebo-controlled trial, should one be warranted. If no serious adverse events which are thought to probably or possibly be due to the study drug AND the cognitive data suggests a trend for possible benefit, then the results of this study will be used to plan a larger follow-up clinical trial.

Children and adults between 3 and 31 years of age with Sturge-Weber syndrome brain involvement and cognitive impairments will be eligible for this pilot study. A total of 10 patients will be enrolled at two centers including Cincinnati Children's Hospital Medical Center and the Kennedy Krieger Institute. This sample size was selected based on 1) availability of potential appropriate subjects at both centers and 2) upon the investigators experience with similar clinical trials.

Cognitive tests proposed have been previously validated in the literature and are normed to aged matched normal controls. These are published tests which are widely used. Therefore, responders in this trial will be subjects whose normed results improve on the task more than what is expected for the increase in age (6 months) +/- expected standard deviation.

Anticipated number of patients to be enrolled:

Table 4

	American Indian or Alaskan Native	Asian or Pacific Islander	Black, not of Hispanic Origin	Hispanic	White, not of Hispanic Origin	Other or Unknown	Total
Female	0	1	1	0	3		5
Male	1	0	0	1	3		5
Total	1	1	1	1	6		10

7. Data Management

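### Each qEEG correlation is called significant at an unadjusted p<0.05 with ten subjects: about a 45% chance of at least one spurious link if 12 tests are null and independent, and moderate correlations are overstated on average when flagged

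*Combined protocol and SAP*

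**What the plan says.** The statistical part of the Synopsis (Section 1, Biomarker Development) uses Spearman's rho to assess the "strength, direction and significance of correlations between qEEG results and neuropsychological outcomes, NeuroQoL and the SWS Neuroscore". The next sentence is the only decision criterion given for these correlations: "Significance will be taken at p<0.05". No multiplicity rule, number of tests, designated pair, sidedness or confidence interval is stated. Nor does the plan say whether baseline, six-month or change values are correlated.

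The neuropsychological panel, in the Synopsis and again in Section 5.3, lists nine NIH Toolbox tests and PROMIS. Section 6 fixes the sample: "A total of 10 patients will be enrolled at two centers". Its basis is practical, not a power calculation: "This sample size was selected based on 1) availability of potential appropriate subjects at both centers", together with the investigators' experience of similar trials.

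Section 2 makes the choice of best outcomes and biomarkers part of the second primary objective. The Synopsis says that the results will help to select outcome measures and biomarkers for a later randomized placebo-controlled trial.

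**The concern.** A 5% rule applied separately to a list of outcomes does not keep the chance of a false finding at 5% for the list. Here the list is not counted, so neither the sponsor nor a later reader can say how surprising one significant correlation would be.

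The second difficulty is the sample size. With ten pairs a correlation must be large before it can reach p<0.05. A genuine moderate association will usually go unflagged, and when it is flagged its estimate will usually be too high. If the significance label guides what is carried into the next trial, the strength of the qEEG link could be misjudged in either direction.

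**Working it through.** The plan gives no error rate, power or critical rho for these correlations, so there is no figure of its own to reproduce beyond the 0.05.

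**Inputs**
- Per-test level 0.05 (Synopsis, Biomarker Development).
- n = 10 (Section 6).
- Tests: 9 Toolbox tests + 1 PROMIS score + 1 Neuro QoL score + 1 neuroscore = 12. This count is an assumption, because the plan states none.
- Two-sided testing, assumed because direction is also to be assessed.
- Ten complete pairs and no ties, assumed.

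**1. Smallest rho that can be significant.** Without ties, rho = 1 − 6Σd²/(n³ − n), and n³ − n = 990 at n = 10. From the exact null distribution:
- Σd² = 58 gives rho = 1 − 348/990 = 0.648, two-sided p = 0.0490.
- Σd² = 60 gives rho = 1 − 360/990 = 0.636, two-sided p = 0.0544.

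The threshold is therefore 0.648 and the true size of each test is 0.0490. If p-values come from the t-approximation, 0.636 also counts as significant and the size is 0.0544. A one-sided exact test would need 0.564. Section 5.7 replaces only withdrawals in the first two months, so there may be fewer than ten pairs. The two-sided threshold is then 0.700 at n = 9, 0.738 at n = 8 and 0.786 at n = 7.

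**2. Chance of at least one false positive, all correlations null, outcomes independent.** 1 − (1 − 0.0490)^k:

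| Tests k | How it could arise | Chance |
|---|---|---|
| 3 | one cognitive score, Neuro QoL, neuroscore | 14.0% |
| 12 | each named measure once | 45.3% |
| 24 | for example, two time points | 70.0% |

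For k = 12 the nominal 0.05 gives 46.0%, and t-approximation p-values give 48.9%.

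**3. Outcomes that correlate with each other.** Twelve outcomes with equal pairwise correlation were simulated against one unrelated qEEG variable (60,000 draws). The chance is about 41% at correlation 0.3, 35% at 0.5, 27% at 0.7 and 17% at 0.9.

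**4. What a significant rho looks like.** Bivariate normal data, n = 10, 100,000 draws, threshold 0.648:

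| True Pearson correlation | True Spearman | Flagged | Mean absolute rho when flagged |
|---|---|---|---|
| 0.3 | 0.29 | 12% | 0.74 |
| 0.5 | 0.48 | 26% | 0.75 |
| 0.7 | 0.68 | 56% | 0.78 |
| 0.8 | 0.79 | 76% | 0.81 |
| 0.9 | 0.89 | 94% | 0.86 |

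The overstatement is large for weak and moderate correlations, small near 0.8 and absent near 0.9.

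**The case against.** The strongest reply is that this is an uncontrolled ten-subject pilot whose results are described as preliminary, and that unadjusted exploratory testing is common in that setting. The plan also asks for strength and direction, so estimates are part of it. That limits the severity. It does not supply a count of tests, an interval or any criterion other than p<0.05.

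Several stronger readings are tempting, and the documents do not support them.

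- A reader might take 12 as a firm minimum, or 45% as a ceiling. It is neither. The Synopsis also speaks of a cognitive functioning score for each subject, in the singular; if that means one composite, there are 3 tests and about 14%. Against this, no composite is defined, the correlation sentence refers to outcomes in the plural, and Section 6 plans to pick the cognitive outcome with the greatest response. Twelve is thus the more natural count. Subscales or extra time points would raise the figure, and correlation among outcomes lowers it.
- Independence is unlikely: the tests share cognitive domains, and cognitive functioning is a component of the neuroscore.
- The global null is not what the plan presumes throughout. The Synopsis reports that qEEG power asymmetry has already been found to correlate with the neuroscore. Without that test, 11 remain, giving about 42% if they are null and independent.
- A reader might infer a 45% chance of adopting a false biomarker. There is one candidate, qEEG power asymmetry, set against several outcomes. The error is a spurious qEEG-outcome correlation.
- A reader might infer that non-significant correlations are discarded. No text says so, and the next paragraph of the Synopsis speaks of using all outcomes to judge responsiveness to sirolimus.
- A reader might infer that any significant rho is overstated. At a true Spearman correlation of 0.89 the flagged estimates average 0.86.

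**Conclusion.** The concern holds as a matter of unadjusted testing and poor information per test. On the 12-test reading, the chance of at least one spurious qEEG-outcome correlation is about 45% if all are null and independent. It is about 27% to 41% for inter-outcome correlations of 0.7 down to 0.3, about 14% if the panel becomes a single score, and higher with added subscales or time points.

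Separately, and without needing every null to be true, a true correlation of 0.5 is flagged about one time in four and its absolute estimate then averages about 0.75. The 0.65 threshold rests on a two-sided exact test, ten complete pairs and no ties. Dropout raises it, a one-sided test lowers it, and ties are plausible for the neuroscore, which runs to a maximum of 15.

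The plan should be changed because biomarker choice is part of a primary objective and p<0.05 is the only criterion stated for these correlations. The issue affects what can be concluded for the next trial, not subject safety.

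**What to change.** Replace the significance sentence in the Biomarker Development paragraph with wording to this effect: all qEEG correlations are exploratory; every rho will be reported with its 95% confidence interval, together with the number of correlations computed; biomarker selection will rest on the estimates and intervals and not on p<0.05. The same paragraph should list the scores and the time point (baseline, six months or change), so that the number is fixed before analysis.

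If one formal test is wanted, name a single pair in advance as the only one tested at 0.05. If that pair uses a cognitive composite, the composite must be defined first. This cures the multiplicity, but not the low power or the overstatement when significant: the single test still needs |rho| of about 0.65. Picking the largest of many estimates also favours overestimates, and reporting the full set with intervals lets a reader see that.

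The cost is one paragraph of text, with no added data or subjects. The downside is that fewer results can be called significant.
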